1 INTRODUCTION

This document describes the additional analysis to be conducted as suggested by EMA Läkemedelsverket in the Type II variation Final Variation Assessment Report on use of Nocdurna with the reference code SE/H/1507/01-02/II/12.

2 REASON FOR ADMENDMENT

This study defines two study populations, a NOCDURNA population and a LUTS population. All patients that are treated with NOCDURNA are defined as a part of the NOCDURNA population, independently of any treatment with LUTS defining drugs. Since there is a degree of overlap between the two populations, some patients will be using both NOCDURNA and LUTS drugs. The protocol and statistical analysis plan clearly defines these patients to be analysed as NOCDURNA patients.

In the Final Variation Assessment Report of the first interim report in this study EMA had the following comment: *The MAH should further discuss the impact of including patients treated with both drugs into the Nocdurna group and consider performing sensitivity analysis with the combination treatment group separated.*

This amendment describe the analysis suggested by EMA.

This amendment will assure a common implementation of the additional sensitivity analysis in the three countries.

3 ANALYSIS SET

In the original statistical analysis plan a new section will be added with the number 5.1.8 on page 20 in the pdf version of the Statistical Analysis Plan stored in REAL (Ferring document management system) dated the 18th of August 2021.

'5.1.8'.

The new treatment groups will be defined in the following.

The protocol specifies in section 9.2 the inclusion and exclusion criteria for the NOCDURNA and LUTS patients and the patients must fulfil these conditions. The extra analysis will divide these patients into three groups where the two first groups will be a division of the NOCDURNA cohort.

- 1) The *combination group* also called *'NOCDURNA and LUTS treated'* of patients must have initiated NOCDURNA treatment at any time during the study period and also a LUTS treatment must have been initiated during the study period.
- 2) The NOCDURNA patients not included in the combination group also called the '*Only NOCDURNA treated*' must have initiated the NOCDURNA at any time during the study period, but not have initiated a LUTS treatment during the study period.
- 3) The patients not included in 1) or 2) above should have initiated a LUTS treatment, but not a NOCDURNA treatment during the study period.

The order of the initialization of the treatments are not considered, and there is no condition about the treatments should be overlapping in time.

The analysis of the events will calculate the incidence rates of the patients in group 1 and 2.

The number of patients in '*NOCDURNA and LUTS treated*' and '*Only NOCDURNA treated*' are presented in the first interim report in table 22 for Sweden and in table 58 for Denmark. There were in total 1606 NOCDURNA patients in Sweden and 741 NOCDURNA patients in Denmark in the first year and the combination group was 63.5% in Sweden and 65.7% in Denmark.

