9.2.3.2 Right censoring events – LUTS cohort

Patients will be followed from the index date to the date of the censoring event: a dispensed prescription for a vasopressin agonist or desmopressin drug, transfer out of the database, emigration, death or end of the study period, whichever occurs first. As appropriate, patient will also be followed from index date to the date of the diagnosis of the outcome of interest, or the end of treatment of drugs defining the LUTS cohort, as defined in section 9.3.1.

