5.1.7 Exclusion criteria – LUTS cohort

The following exclusion criterion will be applied to the LUTS cohort:

- Treatment with vasopressin or any of its analogues (defined as a dispensed prescription within 6 months (180 days) before the index date [index date -1 day]; ATC codes H01BA), irrespective of formulation or dose/strength.
- If a patient according to the above is qualified for both the Nocdurna ® and the LUTS group, this patient's information must be deleted from the LUTS group, since it is expected that the Nocdurna ® group will be the smallest.
- If a prescription for a LUTS drug is found before the study time period, this patient must be excluded, since the later prescriptions will not be the first ever prescription with in study time period.
- Patients with missing information on the variables required for the (key) analyses (i.e. missing information on age and sex) will be excluded.

Figure 1. Inclusion, exclusion and study period start for LUTS treatment as defined above.

This is a safety study (PASS) and all findings are safety related.

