10.2.8 Secondary objective 7: Comparative analyses

Where possible, for the comparative analyses of primary and secondary outcomes of interest, the same analyses (Poisson regression) as in Section 10.1.2 will be applied but now with treatment group (Nocdurna ®/LUTS) as an additional factor. Patients in the two groups will have their exposure time terminated when patients switch treatment (from Nocdurna to LUTS treatment or from LUTS treatment to Nocdurna). To investigate if the incidence rate ratio (IRR) for the Poisson regression of Nocdurna ® to LUTS depend on confounders, treatment by confounder interaction terms will be investigated to see if and to what extent the IRR depend on the respective confounding factor (age class and gender). A SAS macro have been developed for performing the analysis and is documented in 16.2. The output of the analysis is shown in Table 29. The analysis will show the percent change in the Nocdurna ® group as compared with the LUTS group (using the other variables as covariates), the percent change in the age class 65 to <= 75 year and above or equal 75 years as compared with the <65 year age class, and the percent change in the males as compared with the females. Also the 95% CI and the standard error of the means change are calculated, together with the p-value. The scale value for the model is calculated. The LUTS group is used as reference to ease the interpretation. Observe also that the Poisson regression is the same as the Section 10.1.2, but the output is changed to find the incidence rate ratios (IRR) instead of the incidence rates (IR) themselves. If the model does not converge/modelling assumptions are not met, only unadjusted rate ratios will be presented.

10.2.9 Secondary objective 8: Cardiovascular and thromboembolic events of interest resulting in treatment withdrawal

The analysis of this outcome will be performed analogous to that of incident events of symptomatic hyponatraemia in Section 10.1.2, but only for the Nocdurna ® patients. MACE and VTE events considered to be associated with treatment cessation will be those events for which the event date occurs within 14 days prior to the treatment cessation date. Serious MACE and VTE events will be defined as a primary or secondary diagnosis of MACE or VTE recorded in a hospital intensive care unit. This differs from the normal definition of serious adverse event. This can only be evaluated in Sweden.

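### SAP Amendment 1 splits the NOCDURNA cohort by any LUTS drug started in the study period, ignoring order and overlap, so its two rates do not separate combined use from NOCDURNA alone

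*Protocol*

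**What the plan says.** SAP Amendment 1, section 2, reports the regulator's request: discuss the impact of counting patients treated with both drugs as NOCDURNA patients, and consider an analysis that separates the combination group.

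Section 3 then defines the groups.
- Combination group: "must have initiated NOCDURNA treatment at any time during the study period and also a LUTS treatment must have been initiated during the study period".
- NOCDURNA-only patients initiated NOCDURNA, "but not have initiated a LUTS treatment during the study period".
- A third group "should have initiated a LUTS treatment, but not a NOCDURNA treatment during the study period".
- On timing: "The order of the initialization of the treatments are not considered, and there is no condition about the treatments should be overlapping in time".
- On output: "The analysis of the events will calculate the incidence rates of the patients in group 1 and 2".

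Section 4 takes the method from SAP 10.1.2. It is a Poisson model of symptomatic hyponatraemia, with person-time from the index date to the first censoring event. There are separate results for the first month, for later months and for patients aged 65 or over. For this cohort the index date is the first NOCDURNA prescription (SAP 5.1.1).

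**The concern.** A combination-treatment group should contain time during which both drugs were in use. This rule requires neither overlap nor order, and it assigns the group from the whole study period, including time after the index date and after the event.

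Two problems follow. The first is misclassification, which is built into the definition. The second is conditional: a group decided partly by what happens after follow-up starts can be shaped by the outcome. Protocol 9.7.2.1 expects NOCDURNA to be discontinued once symptomatic hyponatraemia is diagnosed. If some of those patients then start a LUTS drug because they stopped, their events move into the combination group. If they become less likely to start one, the shift goes the other way.

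What is at stake is whether the two rates can be read as the rates with and without concomitant LUTS treatment, which is how a reader of the requested analysis would take them.

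**Working it through.** **1. Does any other rule repair the classification?**
- SAP 5.1.3 lists the censoring events for the NOCDURNA cohort. Starting a LUTS drug is not among them.
- SAP 10.2.8 does stop the clock at a switch ("Patients in the two groups will have their exposure time terminated when patients switch treatment"), but it is written for the comparative analyses of secondary objective 7. The amendment uses 10.1.2, which has no such rule.
- SAP 5.1.6 and 5.1.7 treat LUTS initiation as first-ever use and exclude LUTS users from before the study period. On that reading, a NOCDURNA patient still taking an older LUTS prescription has not initiated one in the period and falls into the NOCDURNA-only group. If the amendment means something else by initiation, it does not say so.

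**2. What the rule does to individual patients**

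| Patient | Group under the amendment | Exposure when the event occurs |
|---|---|---|
| Event in month 1 on NOCDURNA alone; LUTS drug first started two years later | Combination, including in the first-month rows | NOCDURNA alone |
| LUTS drug used and stopped within the study period, then NOCDURNA | Combination | NOCDURNA alone |
| LUTS drug begun before the study period and continued, NOCDURNA added | NOCDURNA only (first-ever reading) | Both |

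**3. Size of the group**

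Section 3 gives 63.5% of 1606 patients in Sweden and 65.7% of 741 in Denmark: 0.635 × 1606 ≈ 1020 and 0.657 × 741 ≈ 487. The documents do not say how many of these LUTS starts came before the NOCDURNA index date and how many after.

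**4. Can the rule create a difference where there is none?**

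The simulation used 4 million patients per scenario and no effect of LUTS co-treatment. The inputs are assumptions, not document figures:
- constant true rate of 20 per 1000 person-years;
- uniform entry over 5 years;
- 35% with a LUTS start before index;
- LUTS-start hazard of 0.25 per year;
- mortality of 0.05 per year.

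The LUTS-start hazard after the event was multiplied by a factor. Rates are per 1000 person-years, combination versus NOCDURNA only:

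| Factor after event | Follow-up to study end | Ratio | On-treatment, mean 0.75 year | Ratio |
|---|---|---|---|---|
| about 0 | 15.8 vs 29.2 | 0.54 | 13.5 vs 31.7 | 0.43 |
| 0.5 | 18.3 vs 24.0 | 0.76 | 17.2 vs 25.2 | 0.68 |
| 1 | 20.0 vs 19.9 | 1.00 | 20.0 vs 19.9 | 1.00 |
| 2 | 22.3 vs 14.7 | 1.52 | 23.3 vs 13.7 | 1.70 |
| 3 | 23.7 vs 11.3 | 2.09 | 25.2 vs 10.3 | 2.44 |

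In these runs about 61% of patients fell in the combination group. About 21% to 22% of its person-time came before any LUTS drug (about 33% with on-treatment follow-up). When the same data were split by time-varying LUTS exposure, the ratio was 0.99 to 1.02 in every scenario run.

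**5. How few events matter**

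The amendment declares the numbers in its table shells to be random, so this shows scale only. In Table 1A, 4 / 14.92 × 1000 = 268.1 person-years and 10 / 23.12 × 1000 = 432.5 person-years, and the ratio is 23.12 / 14.92 = 1.55. Move two events from combination to NOCDURNA only and leave person-time as it is: 6 / 268.1 = 22.4 and 8 / 432.5 = 18.5 per 1000, ratio 0.83. With counts of this order, reassigning two events reverses the ranking.

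**The case against.** The strongest reply is that bias has not been shown. With a factor of 1 the ratio is 1.00, so the rule distorts the rates through the outcome only if hyponatraemia changes later LUTS starts, and no section says that it does. Protocol 9.7.2.1 speaks of stopping NOCDURNA, not of starting anything else. LUTS drugs started before the NOCDURNA index date also put a patient in the combination group, and a later event cannot have caused those starts. All of this stands.

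A reader might infer a definite upward bias. For example, if 60% of event-free patients and 70% or 80% of event patients start a LUTS drug, the null ratio is about (0.7/0.3)/(0.6/0.4) = 1.56 or (0.8/0.2)/(0.6/0.4) = 2.67. These figures only return the assumed probabilities, which have no source in the documents. Nor does the 63.5% to 65.7% share measure how many patients are exposed to such a bias.

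It would also go too far to say that the analysis tells the regulator nothing. Removing everyone who ever started both drugs does show how the NOCDURNA rate changes without them. The amendment asks for two rates, with no ratio or test between them.

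Finally, a reader might see support in SAP 5.1.7, where a patient who qualifies for both cohorts has LUTS data removed ("information must be deleted from the LUTS group, since it is expected"), while SAP 10.2.8 truncates at switch. That is a separate and small inconsistency. The amendment calculates no rate for the LUTS group, and SAP 5.1.3 still carries the LUTS censoring rule of Protocol 9.2.3.2.

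None of this answers the misclassification, which needs no assumption about how patients behave after the event.

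**Conclusion.** The point holds for the split of the NOCDURNA cohort in SAP Amendment 1. By definition, the combination group includes sequential users, and NOCDURNA-only time and events before any LUTS start. The NOCDURNA-only group can include concurrent users whose LUTS drug predates the study period; this last part rests on reading initiation as first-ever use, as SAP 5.1.6 and 5.1.7 do.

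Immortal-time bias or reverse causation is possible but not established. Its size and direction cannot be determined from the documents. The simulated ratios are illustrative: they depend on the stated assumptions and on a constant hazard, whereas the protocol expects more hyponatraemia in the first month.

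The reach is one descriptive sensitivity analysis of the primary outcome. The overall NOCDURNA cohort rates do not change. The amendment should be corrected, because the rates as defined cannot be read as rates with and without concomitant treatment.

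**What to change.** Replace the group definitions in Amendment 1, section 3, with one of these:

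1. **Fixed at index.** A patient is co-treated if LUTS supply, built as in SAP 9.1.1 and including drugs begun before the study period, covers the NOCDURNA index date; otherwise the patient is NOCDURNA only. Nothing after the index date affects the group. The price is that later LUTS starters stay in the NOCDURNA-only group.
2. **Time-varying.** Split each patient's NOCDURNA person-time by whether LUTS supply is current, and assign an event to the exposure in force just before it. This matches concomitant use more closely and needs split records in the Poisson input data.

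State in the amendment that overlap is required, and define initiation so that all three countries apply it in the same way.

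The cost is new amendment wording and modest reprogramming. The dispensing dates are already held, because SAP 9.1.1 needs them for exposure periods and SAP 5.1.7 already requires a check for LUTS prescriptions before the study period.

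Separately, reconcile the deletion rule in SAP 5.1.7 with truncation at switch in SAP 10.2.8.

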4 ADDITIONAL SENSITIVITY ANALYSIS

In the original statistical analysis plan a new section will be added into the section with the number '10.1.3 SENSITIVITY ANALYSIS' on page 29 in the pdf version of the Statistical Analysis Plan stored in REAL dated the 18th of August 2021.

'10.1.3'.

An additional sensitivity analysis will be performed analysing NOCDURNA patients divided into two groups, one group defined as 'Only NOCDURNA treated' and the other group as 'NOCDURNA and LUTS treated'. The analysis will be done as described in section 10.1.2 Incidence of symptomatic hyponatraemia' on page 27 in the pdf version of the Statistical Analysis Plan stored in REAL dated the 18th of August 2021. The section describing the analysis is cited below to make this a stand-alone document. Only the primary objective of symptomatic hyponatraemia will be analysed in this sensitivity analysis.

'The incidence rate of the primary outcome reported since index date in the study period will be modelled using a Poisson regression model and expressed as number of cases per 1000 patients years at risk (+- 95% CI) for the Nocdurna ® group and the LUTS contextual cohort, separately. Person-period at risk is defined according to person-time observed from the index date to the first right censoring event. The dependent variable will be number of events for each person and the independent variable will be treatment, age class, and gender. Stratum-specific incidence rates will also be examined giving rates divided by gender, first month after index date and events occurring after the first month after the index date. Also incidence rates for patients with an age above or equal to 65 years will be calculated.'

5 TABLE SHELL

All number in the table are random numbers.

Table 1A extra Sensitivity analysis. High level results of Incidence of symptomatic hyponatraemia in *country*

	Only NOCDURNA treated	Only NOCDURNA treated, Male	Only NOCDUR- NA treated, Female	NOCDURNA and LUTS treated	NOCDURNA and LUTS treated, Male	NOCDURNA and LUTS treated, Female	NOC-DURNA, M+F	NOCDURNA, Male	NOC-DURNA, Female
Number of subjects	663	141	522	943	382	561	1606	523	1083
Number of events	4	1	3	10	3	7	14	4	10
Mean unadjusted rate of	14.92	16.00	14.59	23.12	17.22	27.10	19.98	16.90	21.56
events									
Incidence rate	11.18	N/A	N/A	18.01	N/A	N/A	13.65	13.97	14.45
[95 % CI]	[8.13; 15.36]			[14.32; 22.65]			[12.07; 15.43]	[11.12;17.55]	[12.49;16.71]

Table 2A extraSensitivity analysis. Incidence of symptomatic hyponatraemia in *country*

	Only NOCDURNA treated	Only NOCDURNA treated, Male	Only NOCDURNA treated, Female	NOCDURNA and LUTS treated	NOCDURNA and LUTS treated, Male	NOCDURNA and LUTS treated, Female
Variable, time period and population						
All patients - All exposure time						
Number of subjects	3512	2289	1223	1488	931	557
Number of events	493	367	126	129	93	36
Total person years (y)	510.4	335.7	174.7	219.5	138.4	81.0
Mean unadjusted rate of events (events/1000 person-years)	1201.8	1364.8	896.9	759.7	866.9	580.5
Number of patients with more than 1 event	29	25	4	8	5	3
Number of events in patients with more than 1 event	60	52	8	16	10	6
Number of patients with at least one event	Xx	Xx	Xx	Xx	Xx	Xx

					NOCDURNA and LU	TS
	Only NOCDURNA	Only NOCDURNA	Only NOCDURNA	NOCDURNA and LUTS	treated,	NOCDURNA and LUTS
	treated	treated, Male	treated, Female	treated	Male	treated, Female
Incidence rate (95 % CI)	861.40 (798.94 -	1073.58 (989.55 -	688.70 (608.23 -	532.61 (466.19 -	662.92 (565.25 -	427.68 (341.35 -
	928.74)	1164.75)	779.81)	608.49)	777.46)	535.85)
Standard Error of Mean	33.08	44.64	43.66	36.19	53.91	49.20
Scale - one value for each model	0.7468	0.7796	0.6830			
Events first month after Index date						
Number of subjects	3512	2289	1223	1488	931	557
Number of events	129	98	31	28	18	10
Total person years (y)	491.4	321.7	169.6	214.7	134.5	80.2
Mean unadjusted rate of events	312.8	362.0	220.8	161.9	176.6	137.3
(events/1000 person-years)						
Variance of unadjusted rate	642.4	645.5	636.7	661.6	683.9	625.5
Number of patients with more than 1				1	1	
event						
Number of events in patients with				2	2	
more than 1 event						
Number of patients with at least one	Xx	Xx	Xx	Xx	Xx	Xx
event						
Incidence rate (95 % CI)	221.51 (201.40 -	285.44 (257.50 -	163.73 (139.55 -	112.50 (94.11 -	126.37 (100.58 -	114.02 (87.49 -
	243.62)	316.41)	192.11)	134.48)	158.78)	148.60)
Standard Error of Mean	10.75	15.00	13.35	10.24	14.72	15.41
Scale - one value for each model	0.4641	0.4882	0.4168			
Events after first month and						
onwards						
Number of subjects	2324	1536	788	1017	639	378
Number of events	229	169	60	58	44	14
Total person years (y)	406.1	268.8	137.3	179.2	113.6	65.6
Mean unadjusted rate of events	650.5	720.6	513.7	366.3	415.8	282.7
(events/1000 person-years)						
Variance of unadjusted rate	611.2	610.4	613.6	603.0	619.4	575.3
Number of patients with more than 1	13	11	2	4	3	1
event						

					NOCDURNA and LUT	S
	Only NOCDURNA treated	Only NOCDURNA treated, Male	Only NOCDURNA treated, Female	NOCDURNA and LUTS treated	treated, Male	NOCDURNA and LUTS treated, Female
Number of events in patients with more than 1 event	26	22	4	8	6	2
Number of patients with at least one event	Xx	Xx	Xx	Xx	Xx	Xx
Incidence rate (95 % CI)	513.14 (465.63 - 565.51)	628.77 (565.80 - 698.74)	421.10 (359.52 - 493.23)	297.85 (249.79 - 355.15)	386.66 (314.79 - 474.93)	207.78 (151.08 - 285.75)
Standard Error of Mean Scale - one value for each model	25.44 0.6639	33.85 0.6936	33.97 0.6043	26.74	40.57	33.78
Patients >= 65 years						
Number of subjects	2435	1573	862	1038	650	388
Number of events	379	281	98	100	69	31
Total person years (y)	352.4	230.4	122.0	152.6	96.6	56.0
Mean unadjusted rate of events (events/1000 person-years)	1332	1519	993	843	915	722
Variance of unadjusted rate	648	646	649	646	661	620
Number of patients with more than 1 event	22	19	3	7	4	3
Number of events in patients with more than 1 event	46	40	6	14	8	6
Number of patients with at least one event	Xx	Xx	Xx	Xx	Xx	Xx
Incidence rate (95 % CI)	994.08 (912.02 - 1083.53)	1225.03 (1115.13 - 1345.76)	801.29 (695.41 - 923.29)	616.35 (527.97 - 719.52)	725.40 (600.62 - 876.09)	555.75 (432.23 - 714.58)
Standard Error of Mean	43.70	58.75	57.94	48.67	69.86	71.28
Scale - one value for each model	0.7701	0.7995	0.7140
